## 11.2 Permitting Access to Source Data

The investigational site participating in this study will maintain the highest degree of confidentiality permitted for the clinical and research information obtained from the subjects and donors in this clinical trial. Medical and research records should be maintained at each site in the strictest confidence. However, as a part of the quality assurance and legal responsibilities of an investigation, the investigational site must permit authorized representatives of the sponsor(s) including, pharmaceutical collaborators and their commercial partners, and health authorities to examine (and when required by applicable law, to copy) clinical records for the purpose of quality assurance reviews, audits, and evaluations of the study safety and progress. Unless required by the laws that permit copying of records, only the coded identity associated with documents or with other subject data may be copied (and all personally identifying information must be obscured). Authorized representatives as noted above are bound to maintain the strict confidentiality of medical and research information that is linked to identified individuals. The investigational site will normally be notified before auditing visits occur.

## 12. QUALITY CONTROL AND QUALITY ASSURANCE

The investigator is required to keep accurate records to ensure that the conduct of the study is fully documented.

The sponsor is responsible for regularly reviewing the conduct of the trial, for verifying adherence to the protocol, and for confirming the completeness, consistency, and accuracy of all documented data.

## 12.1 Compliance, Access, Entry and Handling of Study Data

The site PI is required to keep accurate records to ensure that the conduct of the study is fully documented, and to ensure that ECRFs are completed for all subjects according to study guidelines outlined in the study protocol and the Data System Users Instruction Manual.

Access to the data entry screens will be user ID and password protected. Each user will be provided with a unique personal ID and password. The investigational site participating in this study will maintain the highest degree of confidentiality permitted for the clinical and research information obtained from the subjects in this clinical trial. Medical and research records should be maintained at each site in the strictest confidence. However, as part of the quality assurance and legal responsibilities of an investigation, the investigational site must permit authorized representatives of the sponsor(s) and health authorities to examine (and when required by applicable law, to copy) clinical records for the purpose of quality assurance reviews, audits, and evaluations of the study safety and progress. Unless required by the laws that permit copying of records, only the coded identity associated with documents or with other subject data may be copied (and all personally identifying information must be obscured). Authorized representatives as noted above are bound to maintain the strict confidentiality of medical and research information that is linked to identified individuals. The investigational site will normally be notified before auditing visits occur.

All data will be entered, stored, and managed in a relational database supported by database servers at the DCC. The results of all clinical and laboratory evaluations will be maintained in the subjects medical records and the data will be transferred from these source documents directly to the electronic study CRFs. In order to maintain security, all data will be encrypted using the Secure Sockets Layer protocol. This protocol allows an encrypted link to be established between the DCC web server and the computer at each center. In addition, the data will be verified by a series of computerized edit checks, and all relevant data queries will be resolved regularly. All discrepancies will be reviewed, and any resulting queries will be resolved with the site personnel and amended in the database.

All changes made to CRFs will be recorded in an electronic audit trail to allow all data changes in the data system to be monitored and maintained in accordance with federal regulations. Once a CRF is entered into the database and the person entering the data indicates that CRF is complete, any change to that data will be entered into the system's audit trail. The audit trail will record the CRF and variable that is changed, the old value, the new value, the date and time the change was made, reason change was made, and the user ID of the person making the change. Once a change is completed, the data system will re-validate all variables on that CRF. The changed CRF will be required to pass all validity and logic consistency checks. If any edit

Page 110 of 129

criteria fail, the system will generate appropriate queries. The clinical center coordinator will be asked to resolve the questions before the changes are completed.

The change system will allow certified DCC personnel and certified clinical center coordinators to make changes. Changes can be initiated by DCC monitors, DCC coordinators, and certified site personnel. Site personnel can access only the data for their own center. The system will generate weekly summary listings of all changes made to the database, the person making each change, and the reason for each change. These reports will be carefully reviewed by the DCC coordinator to monitor for unnecessary changes and/or problems with the data system.

# 13. ETHICAL CONSIDERATIONS AND COMPLIANCE WITH GOOD CLINICAL PRACTICE

### 13.1 Statement of Compliance

This clinical study will be conducted using cGCP as delineated in *Guidance for Industry: E6 Good Clinical Practice Consolidated Guidance*, and according to the criteria specified in this study protocol. Before study initiation, the protocol and the informed consent documents will be reviewed and approved by an appropriate EC or IRB, and NIAID/NIDDK. Any amendments to the protocol or to the consent materials must also be approved by the IRB/EC and submitted to the applicable Health Authorities before they are implemented.

#### 13.2 Informed Consent and Assent

The informed consent form is a means of providing information about the trial to a prospective subject and allows for an informed decision about participation in the study. All subjects (or their legally acceptable representative) must read, sign, and date a consent form before entering the study, taking study drug, or undergoing any study-specific procedures. Consent materials for subjects who do not speak or read English must be translated into the subjects appropriate language.

The informed consent form must be revised whenever important new safety information is available, whenever the protocol is amended, and/or whenever any new information becomes available that may affect participation in the trial.

A copy of the informed consent will be given to a prospective subject for review. The attending physician, in the presence of a witness, will review the consent and answer questions. The prospective subject will be told that being in the trial is voluntary and that he or she may withdraw from the study at any time, for any reason.

### 13.3 Privacy and Confidentiality

A subject's privacy and confidentiality will be respected throughout the study. Each subject will be assigned a sequential identification number, and these numbers rather than names will be used to collect, store, and report subject information.

# 14. PUBLICATION POLICY

The CIT policy on the publication of study results will apply to this trial.

**Appendix 1: Schedule of Events for CIT-05** 

Time points (specified in Days	SCR	WL/	02	3	7	14	21	28	56	75	120	150	180	270	365	365 post
relative to transplant)		$BL^1$														initial tx
Visit Number	01	02	03	04	05	06	07	08	09	10	11	12	13	14	15	Y1
Visit Windows (specified in days)	N/A	N/A	N/A			+/-3	+/-3	+/-3		+/-5	+/-7	+/-7	+/-7	+/-14	+/-14	+/-14
Equivalent Week/Month	N/A	N/A	N/A	N/A		W2	W3	W4	M2	M2.5	M4	M5	M6	M9	M12	Varies
				GE	NER A	L AS	SESSN	1ENTS	6							
Informed Consent	X 	X 														
Med/Diabetes Hx & Demographics	X															
Evaluation of Inclusion / Exclusion	Χ	Χ														
PAP Smear (females)	Χ	X-yrly														
Mammogram (females >35)	Χ	X-yrly														
Colorectal cancer screen (subj ≥50)	X 															
Retinopathy Evaluation 	Χ	X-yrly														Χ
Physical Exam	X	X-yrly	Χ		Χ	Χ	Χ	Χ	Χ	X	Χ	Χ	Χ	X	X	
QOL		X-q3mo								Χ			X		X	Χ
Chest X-Ray	X	X-yrly													X	
Abdominal US (including Pelvis/Liver)	Χ	X-yrly			Χ										X	
ECG	Χ	X-yrly													X	
Cardiac Stress Test or Angiogram	Χ															
PPD	Χ	X-yrly													X	
AE/Hypoglycemic Events/Toxicity Assess		X	X	X	X	Χ	X	Χ	X	X	X	X	X	X	X	
				CAL L					MENTS				1			
CBC (WBC + Diff & Plat)	Χ	X-q6mo	X		Х	X	X	Χ	X	X	X	X	X	X	X	
Coagulation (PT, PTT, INR)	Χ	X-yrly	Χ													
Chemistry 	Χ	X-q6mo	Χ		Χ	X	Χ	Χ	X	X	X	X	X	X	X	
Lipids	Χ	X-q6mo								X			X	X	X	
Thyroid Function (TSH)	Χ	X-yrly														
Pregnancy test (females)	Χ	X8														
PSA	Χ	X-yrly													X	
Serology  (Hep B, Hep C, HIV, HTLV)	Χ	X-yrly														Χ
EBV IgG	Χ															

Time points (specified in Days relative to transplant)	SCR	WL/ BL¹	02	3	7	14	21	28	56	75	120	150	180	270	365	365 post initial tx
Visit Number	01	02	03	04	05	06	07	08	09	10	11	12	13	14	15	Y1
Visit Windows (specified in days)	N/A	N/A	N/A	N/A	+/-3	+/-3	+/-3	+/-3	+/-7	+/-5	+/-7	+/-7	+/-7	+/-14	+/-14	+/-14
Equivalent Week/Month	N/A	N/A	N/A	N/A	W1	W2	W3	W4	M2	M2.5	M4	M5	M6	M9	M12	Varies
CMV IgG, CMV IgM		X-yrly 														X 
Blood Type		X11														
HLA		Χ														
Crossmatch		X 														
Fasting & post-prandial c-peptide 				X	Χ											
Glucose (immediately post-transplant)			X14													
PRA by flow cytometry		X 														
CENTRAL LABORATORY METABOLIC ASSESSMENTS																
First morning spot urine 	X	X						Χ		X					X	X
GFR	X	X-yrly						Χ		X					X	X
CMV and EBV by PCR 		X				X		Χ	X	X	X	X	X 	X 	X	X
HbA1c	X	X-q3mo								X			X	X	X	X
Fasting serum gluc/c-pep & serum creat	X	Х						Χ	X	X	X	X	X 	X 	X	X
90 min  c-pep/glucose (MMTT)	Χ									X			X	X	X	Χ
Insulin modified FSIGT		X-yrly								X					X	X
			LC	CAL 1	META	BOLI	C ASS	ESSM	IENTS							
Glycemic Stability (CGMS)		X-yrly								X					Χ	X
BSR eCRFs 	X	X-q3mo								Х			Х	Х	Χ	Χ
		CIT0	5-SPE	CIFIC	LOCA	L ME	TABO	LIC A	SSESS	MENTS						
Glucose Potentiated Arginine 										Х					Χ	
Glucose Counter-Regulation		X-yrly											Х		Χ	
CALCULATED METABOLIC ASSESSMENTS																
MAGE		X-q6mo								Х			X	Х	X	Χ
LI	X	X-q6mo								Х			Х	X	Χ	Х
Clarke Score	Х	X-q6mo											Х		Х	Х
	CALCULATED METABOLIC ASSESSMENTS (Con't)															
НҮРО	X	X-q6mo								X			X	X	Χ	X

Time points (specified in Days relative to transplant)	SCR	WL/ BL¹	02	3	7	14	21	28	56	75	120	150	180	270	365	365 post initial tx
Visit Number	01	02	03	04	05	06	07	08	09	10	11	12	13	14	15	Y1
Visit Windows (specified in days)	N/A	N/A	N/A	N/A	+/-3	+/-3	+/-3	+/-3	+/-7	+/-5	+/-7	+/-7	+/-7	+/-14	+/-14	+/-14
Equivalent Week/Month	N/A	N/A	N/A	N/A	W1	W2	W3	W4	M2	M2.5	M4	M5	M6	M9	M12	Varies
Beta Score		Χ								X			X	X	X	X
C-peptide (glucose X creatinine) ratio	Х	Х						Χ	Х	Х	Х	Х	X 	X 	Χ	Х
	IMMUNOSUPRESSION LEVELS															
Sirolimus 24-hour trough levels			Χ	Χ	Χ	Χ	Χ	Χ	X	X	X	X	Χ	Χ	Χ	X
Tacrolimus 12-hour trough levels 				X	X	X	X	Χ	X	X	X	X	X	X	X	Χ
CIT05-SPECIFIC IMMUNOSUPPRESSION LEVELS																
Rituximab PK			X					X					X	X		
HACA evaluation			Χ					Χ					X	X		
MECHANISTIC ASSAYS																
Alloantibody	X	X-q6mo 								X			X	Χ	Χ	X
Autoantibody (GAD, IA-2, IAA)		Х								X			Х	Χ	Χ	X
TAT, C3a, & c-peptide		Х	X25													
			CIT0	5-SPE	CIFIC	MEC	HANI	STIC .	ASSAY	S	_		_			
General B and T cell flow cytometry 		X-q 6 mo			X			X		Х		Х	Х	X	Χ	X
HiD B cell tube 		X-q 6 mo			Χ			Χ				X	Х			Х
CD19+ separation for B cell spectratyping 		Х											Х	Х	Х	
Clone tracking 		X-q3mo			Χ	Χ	Χ	Χ	Х	X	X	X	Х	Χ	Χ	X
T cell ELISpot screen 		X-q6mo								Х			Х	Х	Х	
T cytokine profile 		X-q6mo								Х			Х	Х	X	
B cell ELISpot 		X						Χ					Х			
				P	RCH	IVED	SAMI	PLES								
Serum		Х								X			Х	X	Χ	Х
PBMC & Plasma		Х								Х			Х	Х	X	Χ
RNA		Х								Х			Х	Χ	Χ	Х

 WL = Waiting List. BL = Baseline. Repeat assessments as indicated (i.e. yrly, q3mo), while subject is on the waiting list. All one-time WL/BL assessments should be completed on Day -2 whenever possible, but always prior to start of immunosuppression. For repeat WL/BL assessments, results from test done closest to the start of immunosuppression will be used as the baseline value.

<sup>2 Day 0 = the day of transplant. This SOE applies to the  $1^{st}$ ,  $2^{nd}$ , and  $3^{rd}$  transplant as applicable. The SOE is restarted at Day 0 for each subsequent transplant.

<sup>3 Informed Consent #1 includes information on CIT-07 and CIT-05 protocols.

<sup>4 Informed Consent #2 includes information specific to CIT-05. IC #2 must be signed immediately after randomization.

<sup>5 FOBT (take-home multiple sample method) or FIT w/in last yr, flexible sigmoidoscopy w/in last 5 yrs, double-contrast barium enema w/in last 5 yrs, colonoscopy w/in last 10 yrs. All positive tests should be followed up with colonoscopy.

<sup>6Retinopathy eval includes fundoscopic pictures for WL/BL assessments and Y1. Screening retinopathy evaluation should be done per site-specific standards.

<sup>7 Chemistry includes: Sodium, albumin, magnesium, chloride, potassium, alk phosphatase, total bilirubin, CO2, creatinine, ALT (SGPT), BUN, gamma GT, glucose, AST (SGOT), calcium, phosphorus.

<sup>8 Complete pregnancy test within 72 hours prior to randomization.

<sup>9 Serology includes: HBc Ab, HBs Ab, HBs Ag, HCV Ab, HIV, and HTLV-I/II. Do not repeat Hepatitis B tests if HBs Ab was previously positive.

<sup>10 Repeat only if previous test was negative.

<sup>11 Repeat for subsequent transplant(s).

<sup>12 Sample used for crossmatch may be obtained up to 60 days prior to the start of immunosuppression, as long as there is no evidence of infections or transfusions since the time the sample was drawn. Repeat crossmatch for subsequent transplants.

<sup>13 C-peptide should be done locally and drawn fasting, and twice between 1-3 hours post-prandial on Day 3 and Day 7 post-transplant.

<sup>14 Finger stick glucose should be done locally and drawn every hour for the first 6 hours immediately post-transplant.

<sup>15 Subsequent transplants only. Local result used to determine eligibility for subsequent transplant only.

<sup>16 First morning spot urine includes: albumin, protein, and creatinine.

<sup>17 CMV & EBV by PCR done monthly post-transplant. At the time of a subsequent transplant, a more intensified protocol will be utilized.

<sup>18 If blood drawn locally at Months 7 & 8 (Visits 13a, 13b respectively), sample should be sent from local lab to study site and then shipped to the central laboratory (Univ of Washington for fasting glucose/c-peptide and serum creatinine; University of Alberta for EBV & CMV by PCR).

<sup>19 If blood drawn locally at Months 10 & 11 (Visits 14a, 14b respectively), sample should be sent from local lab to study site and then shipped to the central laboratory (University of Washington for fasting glucose/c-peptide and serum creatinine; University of Alberta for EBV & CMV by PCR).

<sup>20 MMTT should include 60 and 90 minute c-peptide and glucose measurements for the screening visit and as necessary when determining graft failure.

<sup>21 Blood Sugar Record (BSR) eCRF is completed using information gathered from subject diary logs, glucometer download data, and insulin requirements.

<sup>22 C-peptide, glucose creatinine ratio calculated monthly.

<sup>23 Tacrolimus levels will be drawn for CIT-07, and will replace sirolimus levels only in subjects from CIT-05 who cannot tolerate sirolimus and are changed to tacrolimus.

<sup>24For each transplant, complete alloantibody assessment every 6 months and again on Day -2, regardless of the most recent draw. Central PRA result, current within 6 months, is used to determine subject eligibility for first transplant.

<sup>25 TAT, C3a & C-peptide: pre-tx, 15, 60, 180 min post-tx.

<sup>26 General flow cytometry on T and B lymphocyte subsets will be performed using a four-color panel. In order to obtain absolute cell counts and for quality control purposes, a CBC with differential will be performed in parallel with every flow cytometry experiment. General flow will be performed every 6 months while subjects are on the waitlist. In addition to the time points listed in the table above, late time points (months 15, 18, and 21 after the first islets transplant) will be added if the subject is still in study follow-up.

<sup>27 The HiD B cell tube refers to using a large number of different fluorochrome conjugated markers in the same tube (11 colors). High definition flow will be performed every 6 months while subjects are on the waitlist. In addition to the time points listed in the table above, high definition flow will be performed at late time points (months 15, 18, and 21 after the first islets transplant) if the subject is still in study for follow-up.

<sup>28 CD19 separation will be performed twice while subject is on the waiting list prior to transplantation and at least once during a late time point (after 12 months).  DNA will be extracted from peripheral blood leukocytes every three months while subjects are on the waitlist to be transplanted and will be banked at the indicated time points following transplant.

<sup>30 The T cell ELISpot screen will be performed at baseline and repeated every six months while the subject is on the wait list (scheduling can be done at the discretion of other studies and the subject; also, testing will not be performed if the subject has a viral infection.) The screen will be performed using dominant T cell epitopes and pools of peptides for islet antigens. The read-outs will be IFN-γ and TGF-β secretion.

<sup>31If the T cell ELISpot is positive, the specificity of reacting T cells (checked against a panel of peptides) will be profiled and the secretion of different cytokines will be monitored. The sample volume for the T cell ELISpot screen and specificity is 18 ml per time point.

<sup>32 A B cell ELISpot assay will be performed at baseline and repeated every six months while the subject is on the wait list (scheduling can be done at the discretion of other studies and the subject; also testing will not be performed if the subject has a viral infection.) Mononuclear cells will be purified from samples for functional assays and frozen until all samples from a given patient can be performed in the same assay on the same day. 10 ml of anticoagulated whole blood (EDTA) will be required per time point for this assay. Note that the time points have been changed from early to late (BL, M9, M12 and beyond M12, if available.) Later time points are essential because B lymphocyte recovery is expected to be delayed in patients receiving combined B and T cell depleting agents. The 9 month time point will only be assayed if the circulating B lymphocyte count is above 50 B cells per microliter of whole blood. The CIT-07 time points will parallel the time points performed in CIT-05.

<sup>33Subjects requiring >0.1 U/kg insulin will undergo an Arginine Stimulation Test alone (AST).

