#### 1.4.4 Induction Immunosuppression for Subsequent Islet Transplants

The immunosuppressive regimen for subsequent islet transplants will be identical to the regimen for the initial islet transplant with the exception of Thymoglobulin®. Daclizumab or basiliximab will be used instead of Thymoglobulin® for all subsequent islet transplants.

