Intraportal delivery of islets isolated from cadaveric donors will be achieved using a transperitoneal approach through a mini-laparotomy. Islets will be ABO compatible and have a negative serum crossmatch for T lymphocytes, but HLA matching will not be required. It is estimated that >600,000 IEq will be required per recipient at an average of 9,000 IEq/kg of recipient body weight to achieve insulin independence. To optimize the chance of achieving insulin-independence with no more than two procedures, islet preparations  $\geq$ 5,000 IEq/kg will be used for the first infusion, and islet preparations  $\geq$ 4,000 IE/kg will be used for subsequent infusions. The quantity of tissue transplanted will be < 7 mL per infusion. Quality control testing will include assessment of islet purity (> 30%), viability (> 70%), sterility (negative gram stain), and endotoxin content (< 5 IU/kg recipient) prior to release. Functional assessment of islets will also be performed.

Islets will be infused together with heparin and ciproflaxin (70 U/kg) with periodic portal pressure monitoring. Heparin will be continued for 48 hours after the procedure as an intravenous drip with target PPT levels of 50-60 seconds. Following completion of heparin, subjects will be treated with enoxaprin 30 mg subcutaneously bid through day 7.

Subjects who do not meet criteria for insulin-independence at any time after 75 days following the initial transplantation may be eligible for a second transplantation of islets. If the development of panel-reactive anti-HLA antibodies has occurred, only subjects with a PRA ≤ 20% will remain eligible, and both antibody specific and prior mismatched antigens will be avoided. To avoid problems related to Thymoglobulin® sensitization, we will administer daclizumab (2 mg/kg on day 0 followed every two weeks with 1 mg/kg for 4 additional doses) in order to sustain an anti-T lymphocyte induction effect. Should a third infusion of islets occur to achieve insulin-independence, only if the interval between the second and third islet infusions is >10 weeks will an additional course of daclizumab be administered. Rituximab administration will not be repeated with either a second or third infusion of islets.

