#### 3.1.3 Additional Exploratory Endpoints

Section 9 describes the mechanistic assays that will be done. Additional exploratory analyses will generate metabolic and mechanistic hypotheses for further investigation. Each of the following tests allows for the quantification of several metabolic parameters explained in Section 9. End points from subjects in CIT-07 will be compared to subjects from University of Pennsylvania in CIT-05 in Section 10.

- A Glucose-potentiated arginine (GPA) test  $^{11}$  will be conducted at  $75 \pm 15$  days after each transplant and at  $365 \pm 14$  days after the last transplant and the endpoints of acute c-peptide and insulin responses to arginine computed and analyzed.
- Among subjects who are insulin independent, the glucose potentiation slope and  $\beta$ -cell secretory capacity will also be calculated and analyzed at  $75 \pm 15$  and  $365 \pm 14$  days after last transplant.
- Glucose counter-regulation (paired eu- and hypoglycemic clamp studies) $^{68, 69, 154, 155}$  will be conducted pre-transplant and at  $180 \pm 30$  days and  $365 \pm 60$  days after the last transplant.
- Immunophenotyping of lymphocyte subsets will be performed at baseline, days 7 and 28, and months 2.5, 6, 9 and 12.
- HiD (high-resolution multiparameter (flow cytometry) of B lymphocyte subsets will be performed at baseline and on days 7 and 28, and months 5 and 6. These time points were chosen because they are likely to be most informative for analyzing B cell depletion and reconstitution following treatment with anti-CD20.
- B lymphocyte repertoire analysis (CDR3 spectratyping) will be performed on CD19+ cells at baseline, and months 6, 9, and 12. Samples will be collected for clone

tracking analysis at baseline and at all subsequent study time points.

• ELISpot analysis of islet-reactive peripheral blood T Lymphocytes will be performed at baseline, days 0, 7, and 28, and months 2.5, 6, 9, and 12. If the ELISpot is positive, the specificity and cytokine profile of reacting T cells will be characterized in father detail.

• The memory B cell response to influenza will be analyzed at baseline and at month 6.

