# 7.5.1 Criteria and Timing for Subsequent Islet Transplants

Islet transplant recipients who do not meet criteria for insulin independence (see section 3.1), but have either a basal or stimulated c-peptide level  $\geq 0.3$  ng/mL (0.1 nmol/L), will be considered **insulin-dependent with partial islet graft function**, and will be considered for a **second islet islet transplant**. Their insulin requirements will be determined by the total daily dose necessary to maintain the HbA1c  $\leq 7.0\%$ , the fasting capillary glucose level  $\leq 140$  mg/dL (7.8 mmol/L), and the 2-hour post-prandial capillary glucose levels  $\leq 180$  mg/dL (10.0 mmol/L), based on measuring capillary glucose levels a minimum of 21 times in a seven day period, and having at least one MAGE in that week.

In order to be eligible for a second islet transplant the following requirements must be met:

- 1. Subject received ≥5,000 IE/kg with the first transplant, but failed to achieve or maintain insulin independence
- 2. Subject has been compliant with study monitoring and prescribed immunosuppressive therapy
- 3. Subject has no unresolved SAEs
- 4. No evidence of progressive renal dysfunction, with blood creatinine rising above 2.0 mg/dL (177  $\mu$ mol/L)
- 5. No evidence of hypersensitization, allergic responses, or other potentially serious drug reactions to medications required by the protocol
- 6. PRA ≤50% by flow cytometry (assessment performed locally) and the alloantibody specificity not cross-reactive with antigen(s) present in the subsequent islet preparation in order to avoid unacceptable antigen(s).

A second islet transplant will be considered after the  $75 \pm 5$  days visit and metabolic assessment is completed, but before 8 months from the first transplant.

Islet transplant recipients who do not meet the criteria for insulin independence after the first infusion, and have both basal and stimulated c-peptide levels <0.3 ng/mL (0.1 nmol/L), will be considered for a second islet transplant only after review of the potency testing from the first transplant product and post-transplant clinical data by the Steering Committee that will have to give the final approval for the additional islet transplant.

If after the second islet transplant both basal and stimulated c-peptide levels remain <0.3 ng/mL (0.1 nmol/L), these recipients will be considered **failures** with no islet graft function, and immunosuppression will be withdrawn.

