#### 7.7 Visit Windows

The visit for determining the primary endpoint of insulin-independence will occur at  $75 \pm 5$  days following each islet transplant. All other visits are scheduled on a monthly basis from the last transplant (for the first 9 months; quarterly thereafter  $\pm$  14 d until 24 months, then biannually  $\pm$  30 d), and should occur within 7 days (plus or minus) of the calendar date for the transplant. For example, a subject receiving a transplant on the  $14^{th}$  of one month should have follow-up visits between the  $7^{th}$  and  $21^{th}$  of subsequent months. A second transplant resets this schedule, except for the retinal photography.

Study visits should take place within the time limits specified on the Schedule of Events (Appendix 1).

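### Appendix 1 footnote 2 restarts the rituximab PK, HACA, high-definition B-cell and CD19+ spectratyping rows at each re-transplant, although section 3 says rituximab is not repeated (minor)

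*Protocol*

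**What the plan says.** **Restart rule.** Appendix 1, footnote 2, applies the schedule to the first, second and third transplants and adds: "The SOE is restarted at Day 0 for each subsequent transplant". Section 7.7 repeats the rule with one exemption: "A second transplant resets this schedule, except for the retinal photography".

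**Rituximab at later transplants.** Section 3 gives rituximab on Days -2 and +6 of the first transplant and states: "Rituximab administration will not be repeated with either a second or third infusion of islets". Section 1.4.4 reads differently: "The immunosuppressive regimen for subsequent islet transplants will be identical to the regimen for the initial islet transplant with the exception of Thymoglobulin". Section 5.2.2 also makes the later regimen identical apart from listed exceptions, and lists only the IL-2 receptor blocker.

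**Why the B-cell times were chosen.** Section 3.1.3 sets HiD flow at baseline, Days 7 and 28 and months 5 and 6, as likely to be "most informative for analyzing B cell depletion and reconstitution following treatment with anti-CD20".

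**When a re-transplant may happen.** Section 7.5.1 allows a second transplant after the 75 ± 5 day visit and "before 8 months from the first transplant".

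**What stays on the first-transplant clock.** The one-year column (Y1) is fixed at 365 days after the initial transplant and carries general flow, HiD and clone tracking. Footnote 26 says of general flow that "late time points (months 15, 18, and 21 after the first islets transplant) will be added" if the subject is still in follow-up, and footnote 27 says the same of HiD. Rituximab PK, HACA and spectratyping have no Y1 mark.

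**The concern.** Rituximab PK, HACA, HiD flow and spectratyping on sorted CD19+ cells are informative because of their distance from the rituximab dose. If the drug is given once and the schedule restarts at a later transplant, the label Day 28 or Month 6 on such a sample no longer says how long ago the drug was given. Samples planned for particular times after the drug may also never be drawn.

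At stake is the description of B-cell depletion and return, drug clearance and anti-drug antibody timing. Section 3 expects depletion to last more than six months at this dose, so months 5 and 6 lie close to where recovery would be looked for. The affected subjects are those who failed to achieve or maintain insulin independence, so the mistiming is tied to outcome in a study of 12.

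**Working it through.** The plan gives no figure to reproduce. The check is day arithmetic on the schedule.

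**Inputs**
- *s*, the day of the second transplant counted from the first. Earliest: 75 − 5 = 70 (section 7.5.1). Latest: 8 × 365.25/12 = 243.5, taken as 244 (the month length is an assumption). That makes 244 − 70 + 1 = 175 possible days.
- Rituximab on Days -2 and +6 (section 3).
- Rows and windows from Appendix 1. PK and HACA: Days 0, 28, 180, 270. HiD: Days 7, 28, 150, 180, plus Y1. Spectratyping: Days 180, 270, 365. Windows: Day 150 ± 7, Day 180 ± 7, Day 270 ± 14.

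**Formulas**
- A restarted visit of nominal day *d* falls on day *s + d* after the first transplant. That is *s + d + 2* days after the first rituximab dose, or *s + d − 6* after the second.
- A first-clock visit with half-window *w* is displaced if *s < d − w*.

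**Which planned visits are displaced**

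| Row and visit | Window opens | Displaced for *s* | Days out of 175 | Of these, days on which a restarted draw of the same row falls in the window by chance |
|---|---|---|---|---|
| HiD Day 150 | 150 − 7 = 143 | 70–142 | 73 | 22 |
| HiD Day 180 | 180 − 7 = 173 | 70–172 | 103 | 22 |
| PK/HACA Day 180 | 173 | 70–172 | 103 | 15 (*s* = 145–159) |
| PK/HACA Day 270 | 270 − 14 = 256 | 70–244 | 175 | 46 |

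Spectratyping month 6 shares the Day 180 column, so the same limit of 173 applies. Its earliest restarted draw is at 70 + 180 = 250, so none falls in the month 6 window by chance.

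**What the restarted labels mean, in days after the first rituximab dose**
- Day 28: 70 + 28 + 2 = 100 to 244 + 28 + 2 = 274 (planned: 30)
- Day 150: 222 to 396 (planned: 152)
- Day 180: 252 to 426 (planned: 182)
- Day 270: 342 to 516 (planned: 272)

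**Example, re-transplant at Day 80**
- HiD falls at 9, 30, 80 + 7 + 2 = 89, 80 + 28 + 2 = 110, 80 + 150 + 2 = 232 and 80 + 180 + 2 = 262 days. The planned draws at 152 and 182 days are missing, and nothing lies between 110 and 232.
- PK/HACA falls at 2, 30, 82, 110, 262 and 352 days. Nothing lies near the planned 182. The draw at 262 happens to be within 14 days of the planned 272.
- General flow and clone tracking also have a Day 75 visit: 80 + 75 + 2 = 157 days, close to month 5.

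**Example, re-transplant at Day 240.** Days 150 and 180 on the first clock are already past, so no month 5 or 6 sample is lost. The restarted Day 180 draw at 240 + 180 + 2 = 422 days is additional.

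**The case against.** The strongest reply has five parts.

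1. **Not every row moves, and no link to the drug is destroyed.** A reader might infer both from footnote 2. The documents do not support either. The Y1 column, the month 15/18/21 flow samples and retinal photography stay on the first transplant, and elapsed time can be computed from dose and sample dates. This stands as a limit on the concern. It does not remove it, because dates cannot recover a sample that was never drawn.

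2. **The B-cell course is still observed.** General flow has its own CD19+ subset tubes, and in the Day 80 example it and clone tracking are drawn at about day 157. This stands. The gap belongs to HiD, PK, HACA and spectratyping. Re-transplants from Day 173 onward lose no month 5 or 6 sample.

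3. **Bias from pooling by nominal visit is not established.** Nothing states that these assays are pooled across transplants by visit label. Section 10.2.2 foresees longitudinal models, and the time variable is properly left to the SAP.

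4. **The premise is unsettled.** If rituximab is repeated, as sections 1.4.4 and 5.2.2 would allow, the restart matches the dosing. This stands. The contradiction has to be resolved first.

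5. **A rituximab clock for all B-cell rows would do harm.** General flow is one combined B and T cell row, and its restart follows T cells around the new anti-CD25 induction. Footnote 32 wants CIT-07 ELISpot times to parallel CIT-05, where transplant time is the shared clock. Timing from the latest dose would move every sample after Day +6 onto that dose, even in subjects never re-transplanted. This stands and narrows the remedy.

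**Conclusion.** The point holds in a limited form. Footnote 2 and section 7.7, followed as written together with section 3, move the PK, HACA, HiD and spectratyping samples of early re-transplanted subjects off the rituximab clock. The limits are about Day 143 for HiD month 5, about Day 173 for the Day 180 visits, and any re-transplant for PK/HACA Day 270. PK and HACA have no Y1 sample as a substitute.

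This rests on section 3 being the operative rule for rituximab, on footnote 2 being applied literally, and on a second transplant between Days 70 and 244. The documents give no expected number of re-transplants. If 40–50% were insulin independent at Day 75 (an assumption), 12 × 0.6 = 7.2 to 12 × 0.5 = 6 subjects would not be. Fewer of those would meet the other conditions of section 7.5.1, though later loss of independence could add some.

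A reader might infer damage to the trial's main results. The documents do not support that: HiD and spectratyping are exploratory endpoints under section 3.1.3, PK and HACA are not listed as endpoints in section 3, and no primary, secondary or safety endpoint depends on these rows. Severity: minor.

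**What to change.** 1. Reconcile section 3 with sections 1.4.4 and 5.2.2 on whether rituximab is repeated. This review takes no view on which is right.
2. Amend footnote 2, and align section 7.7, so that the rituximab PK, HACA, HiD B-cell and CD19+ spectratyping rows stay on the clock of the transplant with which rituximab was last given. They are not reset by a re-transplant without rituximab, and are drawn at the nearest scheduled visit. This wording works however step 1 is settled.
3. Leave combined B and T cell flow, clone tracking, B-cell ELISpot, graft-function and safety rows restarting as planned.
4. Analyse the B-cell, PK and HACA data by actual days since the first dose of the latest rituximab course.

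**Cost.** One footnote, with draws moved rather than added. After a Day 80 re-transplant, the restarted Day 75 visit is first-clock Day 155, inside 143–157, and can carry the month 5 draw. The month 6 window (173–187) falls on restarted days 93–107, between the scheduled Day 75 and Day 120 visits, so that draw needs a monthly clinic visit or an off-visit sample. HiD draws at Days 7 and 28 after the re-transplant drop out, but general flow still covers B-cell subsets there.
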